## LIST OF ABBREVIATIONS/ACRONYMS

Abbreviation/Acronym	Term
AE	Adverse Event
B+L	Bausch + Lomb
BSCVA	Best Spectacle-Corrected Visual Acuity
CFR	Code of Federal Regulations
CRT	Clinical Research Technician
CRF/e-CRF	Case Report Form / Electronic Case Report Form
EDC	Electronic Data Capture
EC	Ethics Committee
GCPs	Good Clinical Practices
GPRM	Global Pharmacovigilance and Risk Management
IB	Investigator's Brochure
IDE	Investigational Device Exemption
ICF	Informed Consent Form
IRB	Institutional Review Board
TMF	Trial Master File

NOTE: The first occurrence of some abbreviations is not spelled out in the document (e.g., units of measure).

**SYNOPSIS**

Study Title	Orientation Characteristics of kalifilcon A Daily Disposable Toric Contact Lenses Compared to Commercially Available Daily Disposable Toric Contact Lenses
Sponsor	Bausch & Lomb, Incorporated, [name]
Number of Sites	One Investigational Site, Bausch & Lomb Incorporated, [name]
Clinical Phase	Device feasibility
Trial Registration	This study will be registered at clinicaltrials.gov.
Test Articles	
Test Lens: kalifilcon A Daily Disposable Toric [REDACTED] (T01: kali A toric)
 
Comparator Lenses: Commercially available contact lenses                      C01: Total1 for Astigmatism (C01: Total1fA)                      C02: Precision1 for Astigmatism (C02: Precision1fA)                      C03: MyDay Toric (C03: MyDay Toric)

Objective	The objective is to evaluate the contact lens fit characteristics [REDACTED] of kalifilcon A daily disposable toric compared to commercially available Total1 for Astigmatism, Precision1 for Astigmatism and MyDay Toric.
Ethical Considerations	Written approval of the protocol and informed consent will be provided to Bausch + Lomb by the IRB prior to initiation of the study. Investigators are not to deviate from the study protocol except when necessary for the protection of the subject’s health, safety, or welfare. Before any study-specific procedures are performed, the Investigator (or designee) will explain the purpose of the study, the associated procedures, and any anticipated effects or adverse reactions to the subject. The subject will be given sufficient time and opportunity to ask questions regarding any aspect of the study and to decide whether or not to participate in the study. Once the Investigator (or designee) is assured the subject understands the implications of study participation, the subject will be asked to give consent to participate in the study by signing and dating the Informed Consent Form (ICF).
Study Design	
Approximately 30 soft toric contact lens adapted subjects will be enrolled in this feasibility, bilateral, randomized, double-masked (subject and investigator), repeated measures insertion study. All subjects will be seen for a Screening/Dispensing Visit at which informed consent will be obtained and eligibility will be assessed. If subjects satisfy all eligibility criteria, subjects will be dispensed study lenses according to unique randomization tables that will be provided to each Investigator. If study eligibility is met, [REDACTED]
 
[REDACTED]
 
Subjects will be receiving each of the study lens types once, in a randomized order. [REDACTED]
 
[REDACTED]

Study Duration/ Follow-up	
There are a total of 4 study lens types. [REDACTED]
 
Visit 1: Approximately 45 minutes
 
The clinical investigation will take approximately 1 month to complete. Enrollment will take place throughout the duration of the study.

Treatment and Allocation Schedule	
There are a total of 4 study lens types. [REDACTED]

Subjects Planned	
Approximately 30 experienced soft contact lens wearing subjects (includes males and females). Healthy volunteers will be recruited and screened as per criteria outlined below. The subjects will all be experienced soft contact lens wearers.

Anticipated Study Population	
Recruitment for this study will target experienced contact lens wearers that have refractive error requiring contact lens correction. Healthy male and female volunteers will be recruited and screened as per criteria outlined below.

Inclusion Criteria	
To be eligible for entry into the study, the subject must:
 
 
1. Be 18 years or older on the date the Informed Consent Form (ICF) is signed and have capacity to read, understand and provide written voluntary informed consent.
 
2. Have physiologically normal anterior segments not exhibiting clinically significant biomicroscopy findings.
 
3. Have no active ocular disease or allergic conjunctivitis.
 
4. Not be using any topical ocular medications.
 
5. Be willing and able to follow instructions.
 
6. Have signed a statement of informed consent
 

Exclusion Criteria	
The subject is not eligible to participate in the study if the subject is:
 
 
1. Participating in a conflicting study in the opinion of the Investigator.
 
2. Considered by the Investigator to not be a suitable candidate for participation.
 

Disallowed Medications/ Interventions	
Ocular, systemic or topical medications that, in the Investigator's opinion, could potentially affect ocular physiology or performance are prohibited.

Investigational Product, Dosage and Mode of Administration	
Study lenses will be dispensed to subjects meeting all eligibility requirements including any dispensing requirements in this clinical protocol. Study lenses will be worn in office only. The investigator or designee will instruct all subjects to adhere to subject instructions.
 
Subjects will be receiving each of the study lens types once, in a randomized order. The subject will wear each study contact lens pair for approximately 10 minutes.

	[REDACTED]
	[REDACTED]
Pass/Fail Criteria	There are no pass/fail criteria for the results of the clinical investigation.
Interim Analysis	No interim analyses are planned.
Monitoring Risk	The risks involved with contact lens wear in this study will be minimized because the subjects will be examined frequently and at specified intervals. The risks are further minimized by the study eligibility criteria.
Data Quality Assurance	[REDACTED]

## 1.0 INTRODUCTION

The ability of a toric contact lens to orient correctly on-eye and to maintain that orientation [REDACTED] are important aspects of acceptable on-eye performance. Mechanical design features [REDACTED] are components of toric contact lens designs that are added to provide acceptable movement, orientation, and rotational stability needed to correct refractive astigmatism. Study ROC2-23-007 will evaluate [REDACTED] kalifilcon A daily disposable toric compared to Total1 for Astigmatism, Precision1 for Astigmatism, and MyDay Toric.

## 2.0 OBJECTIVE

The objective is to evaluate the contact lens fit characteristics [REDACTED] of kalifilcon A daily disposable toric compared to commercially available Total1 for Astigmatism, Precision1 for Astigmatism, and MyDay Toric.

## 3.0 STUDY DESIGN

### 3.1 Description of Study Design

Approximately 30 soft toric contact lens adapted subjects will be enrolled in this feasibility, bilateral, randomized, double masked (subject and investigator masked), repeated measures insertion study. All subjects will be seen for a Screening/Dispensing Visit at which informed consent will be obtained and eligibility will be assessed. If subjects satisfy all eligibility criteria and none of the exclusion criteria, [REDACTED] in random, successive order according to unique randomization schedules that will be provided to each Investigator.

[REDACTED]

The target is to have 30 subjects who are experienced contact lens wearers complete each study lens type. Further information regarding the target population can be found in the IB.

Visit 1: Approximately 45 minutes

The clinical investigation will take approximately 1 month to complete.

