### **3.2.2 Point of Enrollment and Randomization**

The study is randomized. The study investigator and subject will be masked. An unmasked designee will be responsible for dispensing study products to the subjects according to the randomization schedule. The randomization schedule will be produced prior to study enrollment by Bausch + Lomb's unmasked statistician not otherwise involved in the study.

Randomization will be completed by the unmasked designee. The subjects will be assigned randomization numbers sequentially as they are enrolled. The unmasked designee is responsible for preparing the clinical trial materials according to the randomization schedule. The unmasked designee is also responsible for maintaining study lens inventory, randomization schedule and the Product Accountability Log in a masked fashion.

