### **3.2.3 Subject Completion**

The subject will have completed the study when he/she has worn all of the study lens types. Subjects who require further follow-up due to an ongoing Adverse Event will be followed according to the Adverse Event Section 6.0.

The Investigator may discontinue a subject during the study for any reason if, in his or her opinion, it is in the best interest of the subject. Reasons for discontinuation include but are not limited to:

- adverse effects
- other ocular complications
- subject non-compliance
- subject request
- subject found to be ineligible during study participation\*

\*Any subject enrolled in the study, who later is found to have not met any of the eligibility criteria at entry, will be discontinued at the Sponsor's request.

Subject discontinuations will be documented clearly on the applicable case report form. Subjects that are discontinued from the study following randomization will not be replaced.

Exit visits should be completed for early terminated subjects.

The completion of the clinical investigation shall be deemed to coincide with the last visit of the last subject and when follow-up is complete.

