### **5.1.3 Missed Visits**

If a subject misses a Study Visit, the visit is considered missed, and the subject must be exited from the study. The Investigator or designee must check the missed visit box on the first page of the applicable CRF/e-CRF for that visit.

See Section 3.2.4 Lost to Follow-Up for applicable instructions for subjects who do not return for the final visit.

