### **5.4 Protocol Deviations**

The date of and reason for deviations will be documented in all cases. Significant or major protocol deviations impacting the safety of the subject or the integrity of the study must be reported by the Investigator to the IRB immediately. Reporting of all other protocol deviations must adhere to the requirements of the governing IRB/EC.

Any subject enrolled in the study who later is found to have not met the eligibility criteria at entry will be discontinued. Otherwise, unless the protocol deviations put the subject at risk or the subject's condition requires that they be discontinued from the study, subjects may continue to participate until the end of the study.

All investigators participating in this study agree to conduct the study in accordance with the relevant, current protocol and agree to only make changes in a protocol after being notified by the Sponsor, except when necessary to protect the safety, rights, or welfare of subjects. Under emergency circumstances investigators may proceed without prior approval of the IRB. These deviations will be documented and reported to the IRB as soon as possible. The sponsor will not grant protocol waivers for this study.

Corrective Action plans will be developed and completed as deemed necessary for Investigators who deviate from this protocol in a way that adversely affects the rights, safety or well-being of the subject(s) and/or the quality or integrity of data. The Corrective Action Plan will outline the deviation and the site's corrective and/or remedial actions.

Decisions regarding critical deviations that merit investigator disqualification and will be documented in the Trial Master File.

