## **6.0 ADVERSE EVENTS (AE)**

Subjects who experience an adverse event during study participation will be discontinued from study participation but will be followed by the Investigator until resolution of the adverse event or until the Investigator determines that further improvement is not expected.

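### Does a target of 30 completers conflict with enrolling about 30 subjects and replacing none of them?

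*Combined protocol and SAP*

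**What the plan says.** On enrolment, the Synopsis states "Approximately 30 soft toric contact lens adapted subjects will be enrolled", and Section 3.1 repeats the figure. On completion, Section 3.1 adds "The target is to have 30 subjects who are experienced contact lens wearers complete each study lens type". Section 3.2.3 defines completion: "The subject will have completed the study when he/she has worn all of the study lens types".

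On replacement, Section 3.2.3 states "Subjects that are discontinued from the study following randomization will not be replaced". Section 3.2.2 fixes when a subject becomes randomized: "The subjects will be assigned randomization numbers sequentially as they are enrolled".

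Three rules require an exit:
- Section 6.0: "Subjects who experience an adverse event during study participation will be discontinued from study participation".
- Section 5.4: "Any subject enrolled in the study who later is found to have not met the eligibility criteria at entry will be discontinued".
- Section 5.1.3: "If a subject misses a Study Visit, the visit is considered missed, and the subject must be exited from the study".

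Section 3.2.3 also allows exits at the investigator's discretion or at the subject's request. Section 7.5 restricts every summary other than safety to subjects who were eligible and completed. Section 7.6.3 plans no sensitivity analysis. Sections 7.2 (hypotheses) and 7.3 (sample size) are blacked out, as is a block just before the target sentence in Section 3.1.

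**The concern.** Read literally, the same number serves as both intake and output. If 30 enter and 30 must finish, nobody may leave. Yet the protocol provides several ways to leave, and a subject who has a randomization number cannot be replaced. Because completion means wearing all four lens types and Section 7.5 keeps completers only, a subject who leaves after the third lens drops out of the efficacy summaries for all four.

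The number of completers is the denominator for the primary endpoint, orientation in primary gaze 5 minutes after insertion. Had precision or power been worked out for 30 completers, the figure would be slightly optimistic, and the study report might have to record a missed target after a single exit.

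**Working it through.** **Inputs.** Enrolment is about 30 (Synopsis, Section 3.1). The target is 30 completers (Section 3.1). Replacement after randomization is none (Section 3.2.3). The exit rate per subject, *d*, is not visible anywhere, so it is an assumption, shown from 0.5% to 10%. Exits are treated as independent between subjects.

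**The plan's own figure.** The statistical basis for 30 cannot be reproduced, because Sections 7.2 and 7.3 are blacked out. The only visible link is completers = enrolled × (1 − *d*). It gives 30 × (1 − 0) = 30, so the two figures coincide only if nobody exits.

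**If exactly 30 are enrolled.** Expected completers are 30 × (1 − *d*), and the chance that all 30 complete is (1 − *d*)^30. The last column is the smallest enrolment that gives at least a 90% binomial chance of 30 or more completers.

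| Assumed *d* | Expected completers | Chance all 30 complete | Enrolment for a 90% chance of 30 |
|---|---|---|---|
| 0.5% | 29.9 | 86% | 31 |
| 1% | 29.7 | 74% | 31 |
| 2% | 29.4 | 55% | 32 |
| 5% | 28.5 | 21% | 33 |
| 10% | 27.0 | 4% | 36 |

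A 90% chance with exactly 30 enrolled needs *d* no greater than 1 − 0.9^(1/30) = 0.35%.

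**If a few more are enrolled.** With 31 enrolled and *d* = 1%, the chance of at least 30 completers is 0.99^31 + 31 × 0.01 × 0.99^30 = 0.732 + 0.229 = 0.96. The same calculation gives 0.97 for 32 enrolled at 2% and 0.92 for 33 enrolled at 5%. Each of these enrolments is a fair reading of about 30. At 10%, 33 enrolled gives only 0.58, so the word does not cover every rate.

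**Cost of falling short.** For a given standard deviation, the standard error grows by √(30/*n*):
- 29 completers: √(30/29) = 1.017, or 1.7% wider.
- 28 completers: √(30/28) = 1.035, or 3.5% wider.
- 27 completers: √(30/27) = 1.054, or 5.4% wider.

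**Which rates are plausible.** The documents give no rate, but they do describe the exposure. Each pair is worn for about 10 minutes, in the office only (Synopsis). The one visit listed lasts about 45 minutes (Section 3.1). The subjects are healthy, experienced lens wearers (Section 3.2). Little time is available for an adverse event or a withdrawal, and there is no second listed visit to miss. The low end of the range is the more likely one; nothing in the documents supports 5% or 10%.

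**The case for a change.** The strongest case for a change is that the text offers no visible margin and that one sentence would supply it. Randomization numbers are given at enrolment, so an enrolled subject is in practice one who cannot be replaced. The exit rule in Section 6.0 states no severity threshold. The word for about could allow 33 subjects, but no upper figure is given and the target is a flat 30, so a reader cannot tell whether over-enrolment is intended.

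Part of this stands. The visible text does not show how 30 completers are secured, and Section 3.1 could have said whether 30 is the enrolled or the completed number. The rest is weaker:
- An approximate intake and a target do not contradict each other. A conflict needs the first to be read as exact and the second as a guarantee.
- The rule on late-found ineligibility covers a contingency; it does not forecast one. Sections 3.1 and 4.3 make dispensing depend on meeting all eligibility criteria, and the bar on replacement applies only after randomization, so it does not cover someone who fails screening before receiving a number.
- Section 6.1 limits reportable events to ocular events and serious non-ocular ones, so an exit after every event of any kind is the widest reading of Section 6.0.
- An allowance for attrition may sit in the blacked-out text. Criticising a power or precision figure that cannot be seen would be conjecture.

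**Conclusion.** The arithmetic is right, but it does not show a fault in the plan. With exactly 30 enrolled, a single exit misses the target; at exit rates of 0.5% to 2% that happens with a probability of 14% to 45% (1 − 0.86 and 1 − 0.55). Missing it by one costs 1.7% in the standard error, and missing it by three costs 5.4%. The study is a feasibility study, Section 7.6.1 sets no pass/fail criteria, and no decision in the visible text depends on reaching 30.

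A reworded target would need an attrition rate that the documents do not supply, and it would have to agree with a sample-size section that cannot be read. It would change neither the number recruited, nor the conduct of the visit, nor the analysis set, nor any conclusion. The report will give the actual number of completers in any case, and a reader can judge precision from that. This is a loose statement of a recruitment goal with no gain from changing it.

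The conclusion rests on exits being rare, which the short in-office exposure makes likely but does not prove, and on about 30 leaving room for one to three extra subjects. If exits ran at 10%, the expected number of completers from 30 would be 27. The target would very probably be missed, but the loss of precision would still be about 5%.

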#### **4.3 Instructions for Use and Administration**

Study lenses will be dispensed to subjects meeting all eligibility requirements including any dispensing requirements in this clinical protocol. Subjects will be dispensed an adequate supply of study lenses to complete the study. Lost or damaged study lenses may be replaced at the discretion of the Investigator. An unmasked designee will be responsible for all study lens accountability, including dispensation and collection of study supplies to subjects.

The investigator or designee will instruct all subjects to adhere to the Subject Instructions provided with their study contact lenses.

Subjects will be instructed not to use any other contact lenses or lens care products while wearing the study lenses.

The subjects will be masked to the study lenses. An unmasked designee at each site will be responsible for all study lens accountability, including dispensation and collection of study supplies to subjects.

Subjects will be receiving each of the study lens types once, in a randomized order. The subject will wear a pair of study contact lenses for approximately 10 minutes. See Appendix B for additional Instructions for Use.

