#### **7.4 Randomization**

To minimize or avoid bias, subjects will be assigned randomization numbers as they are enrolled according to unique randomization schedules created for the study. The randomization schedule will be produced prior to study enrollment. Subjects will be receiving each of the study lens types once, in a randomized order.

The randomization schedule is verified up to 5 times during the course of the study: The CRT visually verifies the study material against the randomization schedule during CTM preparation (if applicable) and before dispensing any study materials. The randomization schedule is also verified in EDC after dispensing the CTM. Once the study is complete, randomization is verified again during CTM reconciliation. Upon completion of the study, the EDC programmer also verifies randomization.

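### Do four wears of about 10 minutes fit a visit of about 45 minutes, and does the order of lenses need a stated balancing scheme?

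*Combined protocol and SAP*

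**What the plan says.** The Synopsis states "There are a total of 4 study lens types", and section 7.4 adds "Subjects will be receiving each of the study lens types once, in a randomized order". Wear time appears twice and agrees: the Synopsis has "The subject will wear each study contact lens pair for approximately 10 minutes" and section 4.3 has "The subject will wear a pair of study contact lenses for approximately 10 minutes".

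The only numbered visit with a duration, in the Synopsis and in section 3.1, is "Visit 1: Approximately 45 minutes". Section 3.1 also says "All subjects will be seen for a Screening/Dispensing Visit at which informed consent will be obtained and eligibility will be assessed". A subject finishes only after wearing all four types (section 3.2.3: "The subject will have completed the study when he/she has worn all of the study lens types").

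On order, section 3.1 says "in random, successive order according to unique randomization schedules that will be provided to each Investigator". Section 7.4 refers to schedules prepared before enrolment and names no sequence set. The primary endpoint (section 7.1) is primary gaze orientation 5 minutes after insertion.

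Much of the surrounding text is not public. Parts of the Study Design, Study Duration and Treatment and Allocation rows of the Synopsis, parts of section 3.1, the hypotheses (7.2), the sample size (7.3) and most of Appendix A are blacked out. The procedures under Visit 1 in section 5.1.1 do not appear.

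**The concern.** Read together, the visible figures leave little room. If 40 of 45 minutes are wear, about 5 minutes must hold consent, the anterior-segment check, four pair insertions and removals, and any pause. Either the visit would overrun its stated length, or lenses would follow one another almost at once.

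If lenses are worn back to back, the position of a lens in the sequence, or the lens worn just before it, might affect orientation. Thirty subjects do not divide evenly over four positions (30/4 = 7.5), and no visible text promises balance or a period term. The stakes would be a squeezed procedure on one side, and lens contrasts blurred by order effects on the other.

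**Working it through.** **Time budget**

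Inputs: 4 lens types (Synopsis), about 10 minutes per pair (Synopsis, 4.3), about 45 minutes for Visit 1 (Synopsis, 3.1). The documents give no minutes for consent, screening, handling or intervals, so the 45 can be neither rebuilt nor refuted.

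- Wear: 4 × 10 = 40 minutes, or 40/45 = 89% of the visit.
- Remainder: 45 − 40 = 5 minutes, which is 5/3 = 1.7 minutes per changeover if nothing else took time.
- Effect of the word approximately, with the visit at 45: wears of 8, 9, 11 and 12 minutes leave 13, 9, 1 and −3 minutes. With 10-minute wears and a 50-minute visit, 10 remain.
- With assumed overheads (consent and screening 5 to 20 minutes, handling 1 to 3 minutes per lens) and no pause: 40 + 5 + 4 × 1 = 49 up to 40 + 20 + 4 × 3 = 72 minutes. With 10 to 30 minutes and 2 to 5 minutes instead: 10 + 4 × 12 = 58 up to 30 + 4 × 15 = 90.

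So one sitting would probably overrun on these assumptions, but none of the overheads comes from the documents.

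**Order, if the schedule were 30 unrestricted random permutations (an assumption)**

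- A given lens comes first in 4 or fewer, or 11 or more, of 30 subjects with probability 0.20 (binomial, n = 30, p = 1/4).
- The chance that at least one of the 16 lens-by-position counts is that far out is about 0.92 (simulation). This is the worst of 16 cells, not the typical one.
- One lens directly follows a given other lens 7.5 times on average, with a 95% range of 3 to 12 (simulation).

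**What this costs in precision**

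Let d be a linear drift per period in residual SDs (assumed). The mean squared difference between two distinct positions out of four is (3 × 1 + 2 × 4 + 1 × 9)/6 = 3.333. Without a period term, the standard error (SE) of a paired contrast is multiplied by √((2 + 3.333d²)/2):

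- d = 0.3: √(2.3/2) = 1.07
- d = 0.5: √(2.833/2) = 1.19

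This loss comes from leaving out the period term, not from imbalance. In a balanced Williams square the mean squared position difference is 2.5 for four of the six lens pairs and 5.0 for the other two, so the average is again (4 × 2.5 + 2 × 5.0)/6 = 3.333. Without a period term the same formula then gives:

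| d | pairs with 2.5 | pairs with 5.0 |
|---|---|---|
| 0.3 | √(2.225/2) = 1.055 | √(2.45/2) = 1.107 |
| 0.5 | √(2.625/2) = 1.146 | √(3.25/2) = 1.275 |

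With subject, lens and period in the model, simulated random schedules for 30 subjects were compared with a Williams schedule (seven full blocks of four plus two sequences, so counts of 7 or 8). The Williams schedule narrows the SE of a contrast by about 1.7% on average.

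**The case for a change.** The best argument for acting is that the unredacted numbers must agree with whatever is hidden. The study is conducted in the office and limited to insertion, at one site, with lenses given in succession. All of that fits a single sitting, and a single sitting of about 45 minutes is hard to square with four 10-minute wears plus consent and examination. Section 7.4 carries no redaction mark, and the visible parts of section 7.6 mention no period effect. A reference to the missing text would be cheap.

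The arithmetic stands, and so does the observation that the fit is tight. The rest does not. The blacked-out and absent places are where the number of visits, the spacing and the allocation would be described, so their silence is not an omission by the plan. A randomized order need not mean unrestricted permutations. No analysis model is visible, so a missing period term is not shown. Carry-over into the 5-minute reading is conceivable, but nothing in the documents supports it. Uneven counts are no strong argument either, because a balanced scheme with 30 subjects also yields 7 or 8 per cell.

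**Conclusion.** No change to the plan follows. The visible figures are tight, with about 5 of 45 minutes not taken up by wear. They are not contradictory, since both times are approximate and the detail that could reconcile them is not public. Even if the visit runs long, no result moves: its length is a scheduling estimate, and the primary reading is tied to insertion and lies inside the 10-minute wear.

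On order, randomization removes expected bias from position whether or not the counts are even. Balance buys only precision, about 1.7% of the SE once period is fitted. That is too little to require a particular schedule in a feasibility study that has no pass/fail criteria (section 7.6.1). Fitting period is routine for a four-period within-subject comparison and may already be specified in text that is not public.

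The conclusion rests on 30 completers, one exposure per lens and independent residuals. The 7% to 19% figures need an assumed drift of 0.3 to 0.5 residual SD per period and a model without period, and the documents state neither.
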